Study Objectives	
Primary Objective:
 
 Determine the rate of remission following 1FED vs. 6FED and evaluate the relative efficacy of these dietary therapies 
Secondary Objectives:
 
 To extend Phase 1 of this study with a prospective non-blinded trial that determines the rate of remission following SGC in the 6FED diet non-responders (Phase 2). To extend Phase 1 of this study with a prospective non-blinded trial that determines the rate of remission following 6FED in the 1FED non-responders (Phase 2). To evaluate the effect of each therapy on histological remission defined by a variety of changes in eosinophils, including (a) pre- and post-therapy peak eosinophil counts; (b) partial remission (2-14 peak eosinophils/hpf); and (c) complete histological remission (≤ 1 peak eosinophils/hpf). To evaluate the effect of each therapy by utilizing the histology scoring system (HSS) created to express the severity and extent of other abnormalities in the gastrointestinal (GI) tract that often accompany eosinophilic inflammation. To evaluate endoscopic outcomes as assessed by the endoscopy scoring system (EREFS). To determine the impact of each therapeutic intervention on biomarkers using the EoE Diagnostic Panel (EDP). To evaluate the clinical and psychosocial effect of each therapy utilizing surveys to assess EoE symptoms and problems/feelings related to eating.

	
 • To determine if any clinical parameters predict response to therapeutic intervention. • To determine if any biomarkers including serum food specific IgE, CRD, and IgG4 predict response to therapeutic intervention. • To determine if skin testing, in the form of prick and patch testing, predicts response to therapeutic intervention. • To determine if milk-driven T cells in the blood positively correlate with milk atopy patch test results and effectiveness of dietary therapies. • To bank DNA so that we can later elucidate genetic components of EoE
Study Design	Prospective, non-blinded clinical trial of individuals ages 18-60 years with EoE
Primary Endpoint(s)	The primary endpoint for this study will be the percent of participants who achieve histologic remission (<15 peak eosinophils/HPF) post therapy assessed via endoscopy with biopsy after the end of the 6 week Phase 1.
Secondary Endpoint(s)	
 • Histology and endoscopy measures 
 a. Division of patients into complete (peak eosinophils ≤1/HPF) or partial (≤6 or ≤10) remission b. Histology Scoring system c. Endoscopic scoring system (EREFS) • Biomarkers pre- and post-treatment 
 a. Assessment of EDP Score • Patient Reported Outcome (PRO) metrics pre- and post-treatment 
 a. EoE Adult Symptom Score Activity Index, and Adult EoE Quality of Life Score b. PROMIS General Health Questionnaire • Clinical parameters and biomarkers to predict responsiveness to diet and SGC therapy 
 a. Correlation of clinical characteristics to response to therapy b. Assessment of predictive value of skin prick and patch allergy testing c. Correlation between presence of positive milk component allergy testing to response to 1FED d. Correlation of level of circulating milk-specific T cells with patch testing and response to 1FED e. Predictive biomarker-analysis of EoE transcriptome from EDP analysis on baseline biopsies in correlation to response to treatment.

Sample Size:	136
Study Duration	Minimum 18 weeks to maximum 27 weeks
Inclusion Criteria	
 1. Subject must be able to understand and provide informed consent 2. Have diagnosis of EoE (based on consensus criteria)¹. 3. Are aged 18 to 60 years 4. Have histologically confirmed active disease ≥ 15 eosinophils/hpf in the esophagus within 12 weeks of screening visit 5. Symptomatic (have experienced symptoms within the last month prior to enrollment) 6. PPI confirmation. (As a part of the diagnosis of active EoE, it must be demonstrated that acid reflux disease is not the primary cause of the participant's symptoms by documentation that the participant has been on a high dose of PPI (at least one dose, once daily) for at least 8 weeks prior to a diagnostic endoscopy of EoE without histologic resolution (i.e., ≥ 15 eosinophils/hpf). (Due to the variety of doses and various PPIs available, the dose will be confirmed adequate at the discretion of the PI.) 7. Have a negative urine pregnancy test at screening if of childbearing potential. Females of childbearing potential must have a negative urine pregnancy test (β-hCG) prior to enrollment into the study (i.e., at screening). These participants must agree to use adequate birth control measures (e.g., condom, oral/injectable/subcutaneous contraceptives, intrauterine device, or sexual abstinence) during the study and for at least one month after the last dose of study drug which will be documented in the source documents.
Exclusion Criteria	
 1. Inability or unwillingness of a participant to give written informed consent or comply with study protocol 2. Have been treated with topical swallowed steroids within the last 2 months or systemic steroids within the last 3 months 3. Have pathological eosinophilia in segments of the GI tract other than the esophagus determined by local review 4. Have been diagnosed with a GI malabsorption disorder (i.e., Inflammatory bowel disease, Crohn's disease) or Celiac disease 5. Are currently on dietary therapy strictly avoiding milk or on a 6FED 6. Have concurrent H. pylori gastritis or parasitic infection 7. Have history of anaphylaxis to milk (with current avoidance of milk) 8. Unable to complete study procedures, including EGD. 9. Have previously failed strict dietary therapy clearly documented with one of these regimens or topical steroid treatment (i.e. have not achieved histological remission of <15 eos/hpf after having

	
been on 2 mg of budesonide per day or 1760 mcg of fluticasone per day for 8 weeks prior to the EGD)
 
.
 
 10. Use of investigational drugs within 4 weeks (one month) prior to enrollment 11. Are concurrently receiving any of the prohibited medications listed in section 8.3 12. Not fluent in English 13. On immunotherapy for pollen (if not on maintenance therapy) or IgE-mediated food allergy. 14. Past or current medical problems or findings from physical examination or laboratory testing that are not listed above, which, in the opinion of the investigator, may pose additional risks from participation in the study, may interfere with the participant's ability to comply with study requirements or that may impact the quality or interpretation of the data obtained from the study.

Statistical Considerations (sample size and analysis plan):
	
Conduct a prospective non-blinded randomized trial that compares a 1-food elimination diet (1FED) versus a 6-food elimination diet (6FED) for 6 weeks (Phase 1).
 
Subjects who fail 6FED (i.e. dietary non-responders) in Phase 1 may choose to continue into Phase 2, where they will receive topical swallowed steroid therapy (swallowed fluticasone at a dose of 880 mcg twice a day) for 6 weeks, while on an unrestricted diet. Subjects who fail 1FED will also continue into Phase 2, but they will maintain 6FED for 6 weeks instead of receiving SGC. Participants receiving SGC will return to an unrestricted diet prior to initiating SGC therapy.
 
Empiric dietary therapy interventions are as follows: 1-food elimination diet (1FED)—avoidance of milk vs. 6-food elimination diet (6FED)—avoidance of milk, egg, wheat, soy, fish/shellfish, and peanut/tree nuts, for 6 weeks.

Table of Contents

Glossary of Abbreviations	15
1. INTRODUCTION	17
2. BACKGROUND AND RATIONALE	18
3.1 Background and Scientific Rationale Eosinophilic Esophagitis	18
3.2 Rationale for Selection of Investigational Product or Intervention	19
3.3 Preclinical Experience	19
3.3.1 Previous Research on the Use of Dietary Therapy in Eosinophilic Esophagitis	19
3.4 Clinical Studies	19
3. STUDY HYPOTHESES/OBJECTIVES	20
3.1 Hypotheses	20
3.2 Primary Objectives	20
3.3 Secondary Objective(s)	21
4. STUDY DESIGN	21
4.1 Description of Study Design	21
4.2 Primary Endpoints	23
4.3 Secondary Endpoints	23
4.4 Exploratory Endpoint(s)/Outcome(s)	23
4.5 End of therapy (EOT) and Follow-up	26

1. INTRODUCTION

The primary objective of this proposal is to conduct a prospective, non-blinded randomized trial comparing rates of remission of novel empiric elimination dietary therapies in eosinophilic esophagitis (EoE) in order to assess the therapeutic viability of empiric elimination diets. Moreover, we aim to assess response to topical swallowed steroids in non-responders to empiric six food dietary therapy regimens and the response to 6FED in 1FED non-responders. Participants aged 18 to 60 years with active EoE will be enrolled and the primary efficacy outcome will be the rate of histologic remission assessed using esophageal biopsies obtained following a six week randomized trial of one of two empiric diets. During the screening process, active EoE will be confirmed by histologic evaluation of esophageal biopsies obtained during an esophagogastroduodenoscopy (EGD) in subjects with a history consistent with EoE.

This trial is comprised of a screening (up to 12 weeks in duration) and 2 phases, with each phase lasting 6 weeks. Phase 2 is optional, and eligible participants may choose whether or not to continue into Phase 2. In the first phase, all participants will be randomized 1:1 to either 1 food elimination (milk elimination alone, 1FED) or 6 food elimination (milk, egg, wheat, soy, fish/shellfish, peanut/tree nuts elimination, 6FED) therapeutic diet. At the end of this phase, an EGD will be performed to assess remission. Attainment of remission (esophageal eosinophil counts <15 eosinophils/high powered field) after phase 1 will result in study discontinuation and maintenance of the “successful” dietary therapy. Dietary therapy non-responders who were on 6FED during Phase 1 and choose to continue into Phase 2 will receive topical swallowed steroids for 6 weeks (Phase 2) while on an unrestricted diet, followed by EGD with esophageal biopsies. Dietary therapy non-responders who were on 1FED during Phase 1 and choose to continue into Phase 2 will proceed to 6FED for six weeks (Phase 2) followed by EGD with esophageal biopsies.

The primary efficacy endpoint will assess and compare the percentage of patients achieving remission by following the two diets. Pre- and post-therapy peak eosinophil counts per hpf and percentages of patients that attain histologic remission (<15 eosinophils/hpf) will be reported. The peak eosinophil level refers to the peak eosinophil count from the esophagus as a whole, although peak eosinophil levels are recorded by the esophageal segment. During Phase 1 screening, the peak eosinophil count obtained from local pathology review will be used to assess subject eligibility for study participation. Eligibility for entry into Phase 2 of the study will be determined by the peak count obtained from the central pathology committee's review of the slides. A variety of secondary endpoints, including more detailed histologic and endoscopic scores, novel biomarkers, and several Patient Reported Outcome (PRO) measures will also be assessed. In addition, we will assess the possible value of a variety of clinical characteristics and biomarkers in terms of predicting response to therapy.

This study will provide significant novel information. The use of 6FED after 1FED failure will provide practical information for clinical recommendations. This will be a prospective dietary therapy trial using these empiric elimination diets. As part of our secondary aims, we will also be utilizing a number of novel potential biomarkers to assess their ability in predicting and assessing response to therapy as well as a number of PRO metrics.

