4.2 Primary Endpoints

AIM 1: To determine the efficacy of a 1FED vs. 6FED in EoE.

- a. Primary end-point** The primary efficacy endpoint will be determined at the end of Phase 1 at which time all participants will undergo EGD with biopsy and the percentage of patients who have <15 peak eosinophils/hpf will be determined. The slides will be reviewed by local pathologists for clinical purposes, who will be blinded to the treatment group. The Central Review Pathology Committee (CRPC), who will also be blind to the treatment group, will also review the slides, and the peak eosinophil count from this CRPC review will be used to determine whether or not participants are eligible to continue into Phase 2 of the study. Participants with ≥ 15 peak eosinophils/hpf who were on 6FED during Phase 1 and choose to continue into Phase 2 will receive SGC for six weeks while on an unrestricted diet. Participants with ≥ 15 peak eosinophils/hpf who were on 1FED during Phase 1 and choose to continue into Phase 2 will maintain the 6FED therapeutic diet for 6 weeks. The CRPC will subsequently review the esophageal biopsy slides to determine other parameters (such as the Histology Scoring System (HSS)). CRPC review will be completed, whenever possible, within 2 weeks of a subject's endoscopy. Participants who achieve histologic remission at the end of Phase 1 (as determined by CRPC review) or who complete Phase 1 and opt out of Phase 2 will have completed the study and will resume follow-up care with their primary gastroenterologist or allergist.

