6FED^{14,17,23,24}. Furthermore, we aim to more broadly examine the impact of each therapeutic intervention on other histological parameters associated with EoE using a quantitative histology scoring system (HSS) that has been developed by our expert pathologist, [name]. The HSS evaluates esophageal biopsies for various features (ex: basal layer hyperplasia, dilated intercellular spaces, surface epithelial alteration, apoptotic epithelial cells), eosinophilic inflammation (peak count, eosinophil abscess, eosinophil surface layering), and lamina propria (fibrosis). For central review, slides of relevant esophageal biopsies obtained during the course of the study will be scanned using an Aperio Imaging scanner and viewed by the CRPC using Aperio Imaging Software. Each member of the CRPC has access to an Aperio scanner in his or her pathology department and to the Aperio Imaging Software. Slides may be scanned into Aperio at the local site, or they may be sent to Cincinnati Children's Hospital Medical Center (CCHMC) to be scanned into Aperio (if the local site does not have an Aperio scanner). These slides will be returned to the local site once they have been scanned in. A password-protected website housing the scanned images will be created at CCHMC, and the CRPC will have access to that site. A secure image repository may also be housed at the Data Management Coordinating Center of the Rare Diseases Clinical Research Network at the University of South Florida. The CRPC will establish interobserver and intraobserver variability in their evaluation of eosinophils and other pathologic features: The central pathologists will re-count eosinophils in the scanned images of biopsies and compare the peak eosinophil counts that they obtained by viewing the scanned images to evaluate the variability in the counts. The CRPC pathologists will compare their results amongst themselves and resolve differences via teleconferences in which the scanned images are displayed (meetings hosted by GoToMeeting or equivalent sites). Ten percent intraobserver and interobserver variability will be considered optimum. Each review pathologist will review study slides from subjects enrolled at their own institution ([name], CCHMC; [name], CHCO; [name], NW). Relevant biopsy slides from the other participating sites will also be reviewed by the CRPC. The workload will be distributed as equally as possible among the CRPC pathologists with the assistance of the DMCC. Gastric and/or duodenal biopsies will only be reviewed by local clinical pathologists and will not be sent to the CRPC for review, except for cases where a participant's diagnosis is unclear (for example, when it is unclear whether a potential participant does or does not have eosinophilic gastritis or colitis). In such cases, the CRPC will review gastric and/or duodenal slides to confirm the appropriate diagnosis. Subjects may be included, without stomach or duodenal biopsies, if there is no clinical history of involvement of stomach or duodenum. We hypothesize that HSS will more accurately quantify changes associated with EoE and be reversible following each therapeutic intervention. Furthermore, we hypothesize that some patients may show partial responses, where a subset of the HSS may be improved earlier or in dissociation with eosinophil levels, for example. Finally, we will aim to determine the impact of the various therapeutic interventions on gross endoscopic changes, as determined by a recently developed endoscopy scoring system (EREFS) developed by [name] and colleagues²⁷.

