5.2 Inclusion Criteria

Individuals who meet all of the following criteria are eligible for enrollment as study participants:

1. Subject must be able to understand and provide informed consent
2. Have diagnosis of EoE (based on consensus criteria)¹
3. Are aged 18 to 60 years
4. Have histologically confirmed active disease ≥ 15 eosinophils/hpf in the esophagus within 12 weeks of screening visit
5. Symptomatic (have experienced symptoms within the last month prior to enrollment)
6. PPI confirmation. (As a part of the diagnosis of active EoE, it must be demonstrated that acid reflux disease is not the primary cause of the participant's symptoms by documentation that the participant has been on a high dose of PPI (at least one dose, once daily) for at least 8 weeks prior to a diagnostic endoscopy of EoE without histologic resolution (i.e., ≥ 15 eosinophils/hpf). (Due to the variety of doses and various PPIs available, the dose will be confirmed adequate at the discretion of the PI.)
7. Have a negative urine pregnancy test at screening if of childbearing potential. Females of childbearing potential must have a negative urine pregnancy test (β -hCG) prior to enrollment into the study (i.e., at screening). These participants must agree to use adequate birth control measures (e.g., condom, oral/injectable/subcutaneous contraceptives, intrauterine device, or sexual abstinence) during the study and for at least one month after the last dose of study drug which will be documented in the source documents.

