9. STUDY PROCEDURES

9.1 Screening/Baseline Visit (Weeks -12 to -1)

The screening visit should occur at a maximum of twelve weeks and a minimum of 1 week prior to the enrollment visit. A research staff member will perform the informed consent process. After obtaining informed consent, the following study procedures will be performed and documented:

- Assess eligibility (inclusion and exclusion criteria)
- Collect Medical, surgical and diet history
- Vitals (height, weight, blood pressure, heart rate, respiratory rate, temperature)
- Demographics (age, gender, race)
- Physical exam performed by a study clinician or qualified staff member
- Collect stool sample (if possible) from subjects who have consented to stool collection

- Obtain up to 4 biopsies from the distal and proximal esophagus for research purposes (taken during standard of care EGD)
 - One of these esophageal biopsies will be used for EDP
- Research lab samples
 - Blood (6-10 mL) or saliva (1-2 mL for future genetic testing may be collected at this visit)
 - Blood for metabolomics (3-5 mL)
 - CBC with differential (2-3 mL)- if a CBC with differential was obtained clinically as part of standard of care within the screening period, obtain the results from the standard of care CBC
- Assessment of concomitant medications and therapies
- Pregnancy Test (urine)

Participants may qualify for rescreening if they are ineligible due to any of the reversible illnesses listed in the exclusion criteria if their condition improves while recruitment is ongoing and they still fall within the screening window.

Esophageal biopsies for research may be taken during a participant's standard of care EGD (SOC EGD). If the participant has had an EGD and biopsies performed prior to the screening visit, the results of the EGD may be used to determine eligibility if it falls within the four-week window prior to enrollment. EGDs performed at an outside institution may be used as baseline if the corresponding pathology report and slides are available and the eosinophil counts meet the inclusion criterion of ≥ 15 eosinophils/hpf. In cases where the local pathologist has concerns regarding the eosinophil count, slides may be sent to the CRPC for rapid review in order to verify eligibility.

The amount of blood drawn (clinical plus research) will follow the NIH clinical center guidelines "Guidelines for Limits of Blood Drawn for Research Purposes in the Clinical Center" (May 26 2012).

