**Six Food vs One Food Eosinophilic Esophagitis Elimination Diet
(SOFEEED) Followed by Swallowed Glucocorticoid Trial**

SAP Date: 10/14/2019

NCT02778867

Statistical Analysis Plan
CCHMC Division of Biostatistics and Epidemiology
Data Management and Analysis Center

Six Food vs One Food Eosinophilic Esophagitis Elimination Diet followed by Swallowed Glucocorticoid Trial

Principal Investigator: [name], PhD
Statisticians: [name], TBD

Project Sponsor: NCATS, NIDDK, NIAID
Grant Number (if applicable):
CCHMC IRB Number: 2015-3622
IRB Approval Date(s): Initial (6/23/2015); Current (5/21/2019)

Purpose of Study

The primary objective of this proposal is to conduct a prospective, non-blinded randomized trial comparing rates of remission of empiric elimination dietary therapies in eosinophilic esophagitis (EoE) in order to assess the therapeutic viability of empiric elimination diets. Moreover, we aim to assess response to topical swallowed steroids in non-responders to empiric six food dietary therapy regimens and the response to 6FED in 1FED non-responders. Participants aged 18 to 60 years with active EoE will be enrolled and the primary efficacy outcome will be the rate of histologic remission assessed using esophageal biopsies obtained following a six week randomized trial of one of two empiric diets. During the screening process, active EoE will be confirmed by local pathology review (histologic evaluation) of esophageal biopsies obtained during by esophagogastroduodenoscopy (EGD) in subjects with a history consistent with EoE.

Study design

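### Entry is judged on the local eosinophil count and remission on the central count, with no required fall, so a patient centrally below 15/hpf at baseline can count as a remission without changing

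*Protocol*

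**What the plan says.** **Entry.** Protocol section 5.2 requires the following: "Have histologically confirmed active disease ≥ 15 eosinophils/hpf in the esophagus within 12 weeks of screening visit". The Introduction names the reader: "During Phase 1 screening, the peak eosinophil count obtained from local pathology review will be used to assess subject eligibility for study participation". The SAP agrees under Purpose of Study: "active EoE will be confirmed by local pathology review (histologic evaluation) of esophageal biopsies". The only central check before entry is in Protocol 9.1, and the site decides whether to use it: "In cases where the local pathologist has concerns regarding the eosinophil count, slides may be sent to the CRPC for rapid review".

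**Outcome.** Protocol 3.2 and 13.4.2 define the primary endpoint as a peak count below 15/hpf at the end of Phase 1. No reduction from baseline is required. On the reader, section 4.2 says that "the peak eosinophil count from this CRPC review will be used to determine whether or not participants are eligible to continue into Phase 2", and it describes those who finish after Phase 1 as "Participants who achieve histologic remission at the end of Phase 1 (as determined by CRPC review".

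**Analysis.** Protocol 13.4.1 analyses everyone randomised. The supportive analyses in 13.4.3 are an unadjusted chi-square test, extra covariates, subgroup forest plots, multiple imputation and complete cases. The SAP excludes patients randomised in error who never completed the enrolment visit, and it adds a per-protocol set defined by completing the phase. It lists the baseline eosinophil count as a covariate to consider and has a change-in-count endpoint, but names no reader for either.

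**The concern.** The same cut-off of 15/hpf is applied by one reader at entry and by another at outcome. Any patient read at 15 or more locally but below 15 centrally on the baseline biopsy is eligible, and already meets the outcome definition before starting a diet. If the central count stays below 15, the patient is scored as a remission.

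Selection makes the error one-sided. A local over-read near the cut-off lets a patient in, whereas a local under-read keeps a patient out.

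Two results are at stake. The first is the absolute remission rate on each diet, which is part of the primary objective and is what a clinician will quote. The second is the difference between diets, because patients who count as remissions on either diet add the same amount to both arms and carry no information on the contrast. No planned analysis would show how many such patients there are.

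**Working it through.** **Inputs.** Protocol 13.6 gives remission of 45% on 1FED and 70% on 6FED, two-sided α = 0.05, a likelihood-ratio test, 60 per group for at least 80% power, and 68 per group recruited. The share *m* of randomised patients who are centrally below 15 at baseline is **assumed**, because neither document gives a figure from which to derive it.

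**Step 1: reproduce the plan's figure.** The pooled normal formula for 45% against 70% gives 61 per group. Exact enumeration of the likelihood-ratio test at 60 per group gives 80.6% power. The stated figure is reproduced.

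**Step 2: add the discordant patients.** If a share *m* stays below 15 on either diet, and the rest remit at the planned rate *p*, the observed rate is

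p* = m + (1 − m)·p,

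and the difference becomes (1 − m) × 25 points. For m = 10%:

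- 1FED: 0.10 + 0.90 × 0.45 = 50.5%
- 6FED: 0.10 + 0.90 × 0.70 = 73.0%
- difference: 0.90 × 25 = 22.5 points

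| Assumed m | Patients of 136 | 1FED | 6FED | Difference (points) | Power, 60/group | Power, 68/group, none missing |
|---|---|---|---|---|---|---|
| 0% | 0 | 45.0% | 70.0% | 25.0 | 80.6% | 84.2% |
| 1% | 1.4 | 45.6% | 70.3% | 24.8 | 79.9% | 83.6% |
| 3% | 4.1 | 46.7% | 70.9% | 24.3 | 78.3% | 82.3% |
| 5% | 6.8 | 47.8% | 71.5% | 23.8 | 76.7% | 81.0% |
| 10% | 13.6 | 50.5% | 73.0% | 22.5 | 72.7% | 77.7% |
| 15% | 20.4 | 53.3% | 74.5% | 21.3 | 68.6% | 74.3% |

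If only 80% of these patients stay below 15, the rates rise less. The difference is unchanged, and power is the same or up to about 2 points lower.

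**Step 3: type I error.** If both diets have the same true rate *p*, both arms move to m + (1 − m)·p. They remain equal, so the null hypothesis is preserved.

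**Step 4: cost of restricting the sample.** At m = 15%, 68 × 0.85 = 57.8, or about 58 per group, would have a central baseline of 15 or more. At 45% against 70%, power with 58 per group is 78.6%, against 84.2% for 68 per group with no discordance.

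**The case against.** **The size is not documented. This stands.** A reader might take the statement "Ten percent intraobserver and interobserver variability will be considered optimum" (Protocol 4.3) as evidence of local–central disagreement. It is not. It is a target for variability among the CRPC pathologists when they re-count scanned images. Even if it were borrowed, a central count 10% lower would move only local counts of 15 or 16 below the cut-off (16 × 0.9 = 14.4, but 17 × 0.9 = 15.3), and the documents do not give the distribution of baseline counts. Values of 1% to 3% are as compatible with the text as 10% or 15%. The model also assumes that the planned 45% and 70% are free of this effect, which the documents do not establish.

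**There are safeguards, but they are partial.** Entry also needs a consensus diagnosis, recent symptoms, and eosinophilia persisting after at least 8 weeks of PPI. Outside endoscopies need slides as well as the report. Doubtful counts can go to the CRPC. CRPC members read slides from their own institutions, which may reduce disagreement there. The baseline covariate may absorb some heterogeneity. None of these requires a central baseline of 15 or more, and adjusting for a covariate does not reclassify a patient counted as a remission.

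**Bias towards one diet.** A reader might infer this. The documents point the other way: randomisation is within site and the CRPC is blinded to diet, so such patients should be spread evenly across the arms.

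**Mixed readers in the change endpoint.** A reader might infer that a local baseline will be subtracted from a central week-6 count. The text does not say so. The source of the baseline count is simply not named.

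**Conclusion.** The asymmetry is in the text. Followed exactly, the plan can count a patient who was centrally inactive at baseline as a diet remission, and no planned analysis would reveal it. Both absolute remission rates are pushed up and the difference is pulled towards zero. Neither diet is favoured and type I error is not raised.

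The size cannot be derived from the documents. Over an assumed 1% to 15% of patients, the 1FED rate rises by 0.6 to 8.3 points, the 6FED rate by 0.3 to 4.5 points, and the difference shrinks by 0.3 to 3.8 points. Power at 60 per group falls from 80.6% to between 79.9% and 68.6%. These figures assume that the affected patients stay below 15 on either diet and that everyone else remits at the planned rates. They show sensitivity and do not support a claim that the trial is underpowered.

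The conclusion also takes the primary count to be the central one. That follows from section 4.2, but the SAP names no reader. The point is a worthwhile, cheap improvement and does not undermine the randomised comparison.

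**What to change.** Keep the all-randomised analysis as primary, and add the following to the SAP:

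1. Define the baseline peak count as the CRPC read of the qualifying biopsy, and use it for the covariate and as the starting point of the change endpoint. State that the primary endpoint count is also the CRPC read.
2. Pre-specify a supportive analysis of the primary endpoint, with the same model, limited to randomised patients whose CRPC baseline peak count is at least 15/hpf.
3. Report by arm the number of patients with a CRPC baseline below 15/hpf.

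The restriction uses a biopsy taken before randomisation and read blind to diet, so the supportive comparison remains a randomised one.

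**Cost.** The cost is SAP wording and one extra analysis. It should need no new biopsy or reader. The SAP already plans to use baseline peak count and HSS, the HSS includes the peak count, relevant oesophageal slides go to the CRPC, and outside slides must be available.

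**Limits.** The supportive sample is somewhat smaller. Selecting on a single threshold reading also does not remove regression to the mean, so the restricted rates will be cleaner but not free of upward drift.
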